9.2.2. Exclusion Criteria

Patients meeting any of the following criteria will not be included in the study:

1. Receipt of RZV (comparator cohorts only in the RZV 2-Dose analysis) during the 365 days prior to cohort entry, excluding the cohort entry date;
2. Diagnosis of HZ infection in the 365 days prior to cohort entry, excluding the cohort entry date;
 - Presence of a diagnosis code for HZ infection on the same date as RZV receipt (Dose 1 or Dose 2) will not be cause for exclusion from the study due to the administrative claims process;
3. Receipt of a solid organ transplant or hematopoietic stem cell transplant during the 365 days prior to cohort entry, excluding the cohort entry date;

4. In addition, patients with any of the following claims-based indicators of disease flare during the 91 days prior to cohort entry (as described in Section 9.2.3.2.1 for the RZV 2-Dose analysis, and in Section 9.2.3.2.2 for RZV ≥ 1 Dose analysis) will not be included in the study:
- Emergency room visit or hospitalization with UC as primary diagnosis (UC cohorts);
 - UC-related surgery (ie, colectomy, proctocolectomy) (UC cohorts); and
 - Emergency room visit or hospitalization with RA as primary diagnosis (RA cohorts).

[figure not shown]
In addition, patients meeting any of the following criteria will not be included in the RZV 2- Dose analysis:

5. Diagnosis of HZ infection within 28 days after but not including the cohort entry date (ie, Days [1,28]), as the follow up time will be assessed from day 29 after cohort entry date (Section 9.2.5.1); and
6. Occurrence of any censoring event (ie, disenrollment from health plan, death, end of the study period, or receipt of RZV) within 28 days after cohort entry date (Section 9.2.5.1).

Figure 2 summarizes the schematic for assessing patient eligibility, as well as assessment of covariates and outcomes, for (a) the RZV 2-Dose analysis and (b) the RZV ≥ 1 Dose analysis, with details outlined in the subsequent sections.

Figure 2. Schematic for Assessing Eligibility, Covariates, and Outcomes of RZV Initiators and Comparators in (a) RZV 2-Dose Analysis and (b) RZV ≥ 1 Dose Analysis

(a)

- a. Up to 32 day gaps in medical or pharmacy enrollment allowed
- b. Receipt of RZV exclusion applied to Comparator cohorts only
- c. Baseline conditions included: healthcare utilization, comorbid conditions, and treatment history

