9.3.5.2. Secondary Outcome (Safety)

The secondary outcome for this study is disease flare: UC flare within the UC cohorts and RA flare within the RA cohorts.

For the UC cohorts, the secondary outcome will be defined by an algorithm based on the claims-based indicator of UC flare in the 90 days following the cohort entry date. Based on published literature,^{18,19} the claims-based composite algorithm of UC flare will include a combination of the following components:

- Change in UC therapy (ie, new start or switch);
 - Corticosteroids (oral, rectal, or injection);
 - 5-aminosalicylates (oral or rectal);
 - Immunosuppressants (ie, azathioprine, 6-mercaptopurine, cyclosporine, tacrolimus);
- Emergency room visit with UC as primary diagnosis;

- Hospitalization with UC as primary diagnosis;
- UC-related surgery (ie, colectomy, proctocolectomy).

For the RA cohorts, the secondary outcome will be defined by an algorithm based on the occurrence of a claims-based indicator of RA flare in the 90 days following cohort entry date. Based on published literature,^{20,21,22,23} claims-based composite algorithm of RA flare will include a combination of the following components:

- Change in RA therapy (eg, new start or switch from monotherapy to combination therapy);
 - Corticosteroids (oral or injection): initiation of, or change in, treatment with a short-acting oral glucocorticoid (eg, methylprednisolone 6-day dosing pack) or any parenteral glucocorticoid injection, excluding corticosteroids administered the same day as infusions for RA therapy;
 - Conventional synthetic disease-modifying antirheumatic drugs (csDMARDs) (ie, methotrexate, sulfasalazine, hydroxychloroquine, leflunomide);
- Emergency room visit with RA as primary diagnosis;
- Hospitalization with RA as primary diagnosis.

The claims-based indicators of disease flare will be identified based on drug (NDC and American Hospital Formulary Service [AHFS]), procedure (Healthcare Common Procedure Coding System [HCPCS], CPT[®], and International Classification of Diseases, 10th Revision, Procedure Coding System [ICD-10-PCS]), and diagnosis (ICD-10) codes. The specific codes that will be utilized to identify UC and RA disease flares are provided in [Annex 3](#).

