As patients that have UC and RA may have different clinical characteristics compared to patients that have only one of the two diseases, the number of patients that have both diagnoses will be quantified. Additionally, a sensitivity analysis will be conducted in which the association between RZV exposure and the primary and secondary outcomes is assessed after excluding patients with both UC and RA from the exposure cohorts.

To assess the effect of prior Zostavax vaccination on subsequent RZV effect, an analysis will be performed where the study population is restricted to patients with at least 5 years of enrollment prior to cohort entry. Within this subset, the analysis will be conducted separately among patients with and without Zostavax vaccination during this baseline 5-year period. The effect of prior Zostavax exposure will be informed by the extent to which the estimate of RZV effect differs according to strata of prior Zostavax exposure.

It is possible that the comparator cohorts could include patients previously vaccinated with RZV more than 365 days earlier. To address this potential exposure misclassification, a sensitivity analysis will be performed, for which the study population will be restricted to patients with enrollment that extends back to 20 October 2017 and who do not have any prior administration of RZV during that time. Finally, a sensitivity analysis will be conducted for HZ in which patients are stratified based on their amount of available follow-up time.

Misclassification of disease flares is possible when using claims-based algorithms (for example, patients may change therapy for reasons other than disease flares), leading to over- or under-estimation of the outcome; thus, alternative definitions will be explored and outlined in the SAP as sensitivity analyses. Specifically, sensitivity analysis will explore using a more conservative definition based on only UC-related surgeries or ER and hospitalizations with UC or RA as the primary diagnosis, as well as evaluating more expansive definitions inclusive of other medications of interest, such as biologics or other JAK inhibitor treatments.

Additional sensitivity analysis may be performed if needed.

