ANNEX 3. ADDITIONAL INFORMATION

HCPCS, AHFS, NDC, CPT^{®4} and ICD-10-PCS Codes for Secondary Outcomes

The following code lists will be used for the claims-based indicators of disease flare, as described in Section 9.3.5.2.

Codes for ulcerative colitis disease flare

Corticosteroids (oral, rectal, or injection)

Code type	Code	Description
HCPCS	J0702	INJECTION, BETAMETHASONE ACETATE 3MG AND BETAMETHASONE SODIUM PHOSPHATE 3MG
HCPCS	J0810	INJECTION, CORTISONE, UP TO 50 MG
HCPCS	J0704	INJECTION, BETAMETHASONE SODIUM PHOSPHATE, PER 4 MG
HCPCS	J1020	INJECTION, METHYLPREDNISOLONE ACETATE, 20 MG
HCPCS	J1030	INJECTION, METHYLPREDNISOLONE ACETATE, 40 MG
HCPCS	J1040	INJECTION, METHYLPREDNISOLONE ACETATE, 80 MG
HCPCS	J1094	INJECTION, DEXAMETHASONE ACETATE, 1 MG
HCPCS	J1100	INJECTION, DEXAMETHASONE SODIUM PHOSPHATE, 1MG
HCPCS	J1700	INJECTION, HYDROCORTISONE ACETATE, UP TO 25 MG
HCPCS	J1710	INJECTION, HYDROCORTISONE SODIUM PHOSPHATE, UP TO 50 MG
HCPCS	J1720	INJECTION, HYDROCORTISONE SODIUM SUCCINATE, UP TO 100 MG
HCPCS	J2650	INJECTION, PREDNISOLONE ACETATE, UP TO 1 ML
HCPCS	J2920	INJECTION, METHYLPREDNISOLONE SODIUM SUCCINATE, UP TO 40 MG
HCPCS	J2930	INJECTION, METHYLPREDNISOLONE SODIUM SUCCINATE, UP TO 125 MG
HCPCS	J3300	INJECTION, TRIAMCINOLONE ACETONIDE, PRESERVATIVE FREE, 1 MG
HCPCS	J3301	INJECTION, TRIAMCINOLONE ACETONIDE, NOT OTHERWISE SPECIFIED, 10 MG
HCPCS	J3302	INJECTION, TRIAMCINOLONE DIACETATE, PER 5MG
HCPCS	J3303	INJECTION, TRIAMCINOLONE HEXACETONIDE, PER 5MG
HCPCS	J7506	PREDNISONE, ORAL, PER 5MG
HCPCS	J7509	METHYLPREDNISOLONE ORAL, PER 4 MG
HCPCS	J7510	PREDNISOLONE ORAL, PER 5 MG
HCPCS	J8540	DEXAMETHASONE, ORAL, 0.25 MG
HCPCS	J1095	INJECTION, DEXAMETHASONE ACETATE, PER 8 MG
HCPCS	J1690	INJECTION PREDNISONE, up to 20MG
HCPCS	J2640	INJECTION PREDNISOLONE, up to 20MG
HCPCS	J3304	INJECT TRIAMCINOLONE ACETONIDE PF ER MS F 1 MG
HCPCS	J7312	INJECTION DEXAMETHASONE INTRAVITREAL IMPL
HCPCS	S0173	DEXAMETHASONE, ORAL, 4MG
HCPCS	J7512	Prednisone, immediate release or delayed release, oral
AHFS	680400	Adrenals*
AHFS	68040000	Adrenals*

* Restrict to those with oral, rectal, or injection routes of administration.

⁴ CPT copyright 2022 American Medical Association. All rights reserved.
PFIZER CONFIDENTIAL

5-aminosalicylates (oral or rectal)

NDC	Description
43353088479	APRISO 0.375G CAP ER 24H
54868615000	APRISO 0.375G CAP.SR 24H
65649010302	APRISO 0.375G CAP.SR 24H
00149075206	ASACOL 400 MG TABLET DR
00430075227	ASACOL 400 MG TABLET DR

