Code Type	Code	Description
CPT ⁶	45121	Proctectomy, complete (for congenital megacolon), abdominal and perineal approach; with subtotal or total colectomy, with multiple biopsies
ICD-10-PCS	0DBE0ZZ	Excision of Large Intestine, Open Approach
ICD-10-PCS	0DBE3ZZ	Excision of Large Intestine, Percutaneous Approach
ICD-10-PCS	0DBE4ZZ	Excision of Large Intestine, Percutaneous Endoscopic Approach
ICD-10-PCS	0DBE7ZZ	Excision of Large Intestine, Via Natural or Artificial Opening
ICD-10-PCS	0DBE8ZZ	Excision of Large Intestine, Via Natural or Artificial Opening Endoscopic
ICD-10-PCS	0DBF0ZZ	Excision of Right Large Intestine, Open Approach
ICD-10-PCS	0DBF3ZZ	Excision of Right Large Intestine, Percutaneous Approach
ICD-10-PCS	0DBF4ZZ	Excision of Right Large Intestine, Percutaneous Endoscopic Approach
ICD-10-PCS	0DBF7ZZ	Excision of Right Large Intestine, Via Natural or Artificial Opening
ICD-10-PCS	0DBF8ZZ	Excision of Right Large Intestine, Via Natural or Artificial Opening Endoscopic
ICD-10-PCS	0DBG0ZZ	Excision of Left Large Intestine, Open Approach
ICD-10-PCS	0DBG3ZZ	Excision of Left Large Intestine, Percutaneous Approach
ICD-10-PCS	0DBG4ZZ	Excision of Left Large Intestine, Percutaneous Endoscopic Approach
ICD-10-PCS	0DBG7ZZ	Excision of Left Large Intestine, Via Natural or Artificial Opening
ICD-10-PCS	0DBG8ZZ	Excision of Left Large Intestine, Via Natural or Artificial Opening Endoscopic
ICD-10-PCS	0DBK0ZZ	Excision of Ascending Colon, Open Approach
ICD-10-PCS	0DBK3ZZ	Excision of Ascending Colon, Percutaneous Approach
ICD-10-PCS	0DBK4ZZ	Excision of Ascending Colon, Percutaneous Endoscopic Approach
ICD-10-PCS	0DBK7ZZ	Excision of Ascending Colon, Via Natural or Artificial Opening
ICD-10-PCS	0DBK8ZZ	Excision of Ascending Colon, Via Natural or Artificial Opening Endoscopic
ICD-10-PCS	0DBL0ZZ	Excision of Transverse Colon, Open Approach
ICD-10-PCS	0DBL3ZZ	Excision of Transverse Colon, Percutaneous Approach
ICD-10-PCS	0DBL4ZZ	Excision of Transverse Colon, Percutaneous Endoscopic Approach
ICD-10-PCS	0DBL7ZZ	Excision of Transverse Colon, Via Natural or Artificial Opening
ICD-10-PCS	0DBL8ZZ	Excision of Transverse Colon, Via Natural or Artificial Opening Endoscopic
ICD-10-PCS	0DBLFZZ	Excision of Transverse Colon, Via Natural or Artificial Opening With Percutaneous Endoscopic Assistance
ICD-10-PCS	0DBM0ZZ	Excision of Descending Colon, Open Approach
ICD-10-PCS	0DBM3ZZ	Excision of Descending Colon, Percutaneous Approach

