ICD-10-PCS	0DBM4ZZ	Excision of Descending Colon, Percutaneous Endoscopic Approach
ICD-10-PCS	0DBM7ZZ	Excision of Descending Colon, Via Natural or Artificial Opening
ICD-10-PCS	0DBM8ZZ	Excision of Descending Colon, Via Natural or Artificial Opening Endoscopic
ICD-10-PCS	0DBN0ZZ	Excision of Sigmoid Colon, Open Approach
ICD-10-PCS	0DBN3ZZ	Excision of Sigmoid Colon, Percutaneous Approach

⁶ CPT copyright 2022 American Medical Association. All rights reserved.

Code Type	Code	Description
ICD-10-PCS	0DBN4ZZ	Excision of Sigmoid Colon, Percutaneous Endoscopic Approach
ICD-10-PCS	0DBN7ZZ	Excision of Sigmoid Colon, Via Natural or Artificial Opening
ICD-10-PCS	0DBN8ZZ	Excision of Sigmoid Colon, Via Natural or Artificial Opening Endoscopic
ICD-10-PCS	0DTE0ZZ	Resection of Large Intestine, Open Approach
ICD-10-PCS	0DTE4ZZ	Resection of Large Intestine, Percutaneous Endoscopic Approach
ICD-10-PCS	0DTE7ZZ	Resection of Large Intestine, Via Natural or Artificial Opening
ICD-10-PCS	0DTE8ZZ	Resection of Large Intestine, Via Natural or Artificial Opening Endoscopic
ICD-10-PCS	0DTP0ZZ	Resection of Rectum, Open Approach
ICD-10-PCS	0DTP4ZZ	Resection of Rectum, Percutaneous Endoscopic Approach
ICD-10-PCS	0DTP7ZZ	Resection of Rectum, Via Natural or Artificial Opening
ICD-10-PCS	0DTP8ZZ	Resection of Rectum, Via Natural or Artificial Opening Endoscopic

Codes for rheumatoid arthritis disease flare

Corticosteroids (oral or injection)

Code type	Code	Description
HCPCS	J0702	INJECTION, BETAMETHASONE ACETATE 3MG AND BETAMETHASONE SODIUM PHOSPHATE 3MG
HCPCS	J0810	INJECTION, CORTISONE, UP TO 50 MG
HCPCS	J0704	INJECTION, BETAMETHASONE SODIUM PHOSPHATE, PER 4 MG
HCPCS	J1020	INJECTION, METHYLPREDNISOLONE ACETATE, 20 MG
HCPCS	J1030	INJECTION, METHYLPREDNISOLONE ACETATE, 40 MG
HCPCS	J1040	INJECTION, METHYLPREDNISOLONE ACETATE, 80 MG
HCPCS	J1094	INJECTION, DEXAMETHASONE ACETATE, 1 MG
HCPCS	J1100	INJECTION, DEXAMETHASONE SODIUM PHOSPHATE, 1MG
HCPCS	J1700	INJECTION, HYDROCORTISONE ACETATE, UP TO 25 MG
HCPCS	J1710	INJECTION, HYDROCORTISONE SODIUM PHOSPHATE, UP TO 50 MG
HCPCS	J1720	INJECTION, HYDROCORTISONE SODIUM SUCCINATE, UP TO 100 MG
HCPCS	J2650	INJECTION, PREDNISOLONE ACETATE, UP TO 1 ML
HCPCS	J2920	INJECTION, METHYLPREDNISOLONE SODIUM SUCCINATE, UP TO 40 MG
HCPCS	J2930	INJECTION, METHYLPREDNISOLONE SODIUM SUCCINATE, UP TO 125 MG
HCPCS	J3300	INJECTION, TRIAMCINOLONE ACETONIDE, PRESERVATIVE FREE, 1 MG
HCPCS	J3301	INJECTION, TRIAMCINOLONE ACETONIDE, NOT OTHERWISE SPECIFIED, 10 MG

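### Annex 3 fixes the flare codes but includes an eye implant as a flare steroid, an operation labelled for congenital megacolon, and 22 Excision codes not shown to be colectomy

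*Protocol*

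**What the plan says.** Section 9.3.5.2 names surgery as one component of the UC flare algorithm: "UC-related surgery (ie, colectomy, proctocolectomy". Because it is introduced by 'ie', the definition reads as closed. Section 9.2.2 uses the same component, over the 91 days before cohort entry, as part of exclusion criterion 4: "UC-related surgery (ie, colectomy, proctocolectomy) (UC cohorts". Section 9.7.4 uses it again in the strict flare definition, "using a more conservative definition based on only UC-related surgeries or ER and hospitalizations".

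The codes are not left to the SAP. Section 9.3.5.2 states: "The specific codes that will be utilized to identify UC and RA disease flares are provided in" Annex 3.

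Annex 3 then lists, among others:

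- under UC-related surgery, ICD-10-PCS rows such as "Excision of Large Intestine, Via Natural or Artificial Opening Endoscopic", and a CPT row (45121) that begins "Proctectomy, complete (for congenital megacolon), abdominal and perineal approach";
- in the same list, whole-organ rows such as "Resection of Large Intestine, Open Approach", for the large intestine and the rectum only;
- under corticosteroids, in both the UC and the RA lists, J7312: "INJECTION DEXAMETHASONE INTRAVITREAL IMPL".

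**The concern.** A claims-based outcome is what its code list says it is. If the list admits claims that are not colectomy, not UC-related, or not systemic or bowel-directed steroid treatment, events unrelated to a flare can enter the outcome.

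The surgery rows matter in three places: the UC flare composite, the pre-entry exclusion, and the conservative definition. Section 9.7.4 proposes that last definition because therapy changes may not reflect flares, so it is meant to be the more specific one and should not rest on loosely specified surgery codes. J7312 matters in the main composite for both diseases. The conservative definition drops medications, so J7312 does not affect it.

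**Working it through.** No power or sample-size figure is involved. The check is a tally of Annex 3 against Sections 9.2.2 and 9.3.5.2.

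**Surgery list, by code type**

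- CPT: 25 codes.
- ICD-10-PCS: 36 Excision + 8 Resection = 44.
- Total: 25 + 44 = 69.

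**Excision codes, by approach.** Seven body parts are listed: large intestine, right, left, ascending, transverse, descending and sigmoid.

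| Approach | Codes |
|---|---|
| Natural or artificial opening, no endoscope | 7 |
| Natural or artificial opening, endoscopic | 7 |
| Natural or artificial opening with percutaneous endoscopic assistance (transverse colon only) | 1 |
| Percutaneous | 7 |
| Open, or percutaneous endoscopic | 14 |
| Sum | 36 |

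Natural or artificial opening in any form: 7 + 7 + 1 = 15. Adding the percutaneous rows gives 15 + 7 = 22 codes. None of these descriptors mentions colectomy, and the annex itself lists Excision and Resection as different operations.

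**Resection codes.** Four for the large intestine and four for the rectum: 4 + 4 = 8. The other six body parts have Excision rows and no Resection row. On the ICD-10-PCS rows alone, excision of the sigmoid counts as UC surgery and resection of the sigmoid does not.

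**CPT coverage of segmental surgery.** Open partial colectomy: 44140, 44141, 44143 to 44147 and 44160, which is 8. Laparoscopic: 44204 to 44208, which is 5. Together 8 + 5 = 13. A segmental colectomy is therefore missed only if it leaves no CPT claim.

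**Diagnosis condition.** The emergency-room and hospitalization components require UC as primary diagnosis. Annex 3 attaches no UC diagnosis to any surgery code, so nothing in the list screens out a procedure done for another reason.

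**CPT 45121.** The full descriptor includes subtotal or total colectomy, so the operation fits the procedure named in Section 9.3.5.2. The indication in the descriptor, congenital megacolon, does not fit the UC-related part.

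**J7312.** The UC list is headed oral, rectal or injection, and the RA list oral or injection. The footnote restricting route is attached by asterisk to the two AHFS rows only. J7312 is an HCPCS row, so the restriction does not apply to it. Section 9.3.5.2 defines a new start as a listed medication with none of the same in the prior 365 days. A first implant can therefore register as a new-start steroid in either disease.

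**The case against.** The other side has several good points.

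- A reader might infer that segmental colectomies are missed. They are not missed in general: Section 9.3.5.2 draws on CPT and ICD-10-PCS together, and 13 CPT codes cover them. The gap is confined to ICD-10-PCS.
- A reader might infer that the 22 Excision codes are certainly not colectomies. The descriptors do not prove that. Reading them as biopsy or polyp removal needs coding conventions that the protocol does not give. The list also has Resection of the large intestine through a natural opening, and CPT 44147 is a partial colectomy with a transanal element, so the approach alone decides nothing.
- A reader might say J7312 contradicts its heading. It is labelled an injection, so literally it does not. The fault is an ocular route that nothing screens out.
- CPT 45121 does include a colectomy, and nothing suggests such claims are common in adults with UC on tofacitinib.
- Sections 9.7.4 and 9.9 already admit flare misclassification and promise alternative definitions. The same codes apply to vaccinated and comparator cohorts, and nothing in the protocol points to differential error.

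These points narrow the concern and keep it minor. They do not remove it. The codes are fixed in this document, and the promised conservative definition still rests on UC-related surgery, for which Annex 3 gives the only code list.

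**Conclusion.** The point holds as a code-list error of low severity. J7312 does not belong among flare steroids. CPT 45121 is not UC-related on its face. The 22 Excision codes have not been shown to meet the closed definition of colectomy or proctocolectomy. The ICD-10-PCS rows treat Excision and Resection of six colon segments inconsistently.

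The size cannot be computed, because the protocol gives no frequency for any of these codes. The effect is probably small; that is a judgement, not a result. It would be tempting to express it as a share of events in the conservative definition, but any such percentage would rest on invented counts.

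The reach is limited to the secondary flare outcome and, for the surgery codes, the conservative sensitivity analysis and exclusion criterion 4. The last assumes that the criterion uses the Annex 3 surgery list: it names the same component, and no other list is given. Through that criterion the surgery codes can affect who enters the UC cohorts, including those for the 2-dose analysis. The definition of the herpes zoster outcome is untouched.

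**What to change.** In Annex 3, before programming:

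1. Delete J7312 from both the UC and the RA corticosteroid lists.
2. Delete CPT 45121.
3. Remove the 15 natural-opening and 7 percutaneous Excision codes from the UC-surgery list unless each is shown to represent colectomy. If any are kept, record the reason and state whether the claim must carry a UC diagnosis.
4. Add Resection codes for the right, left, ascending, transverse, descending and sigmoid colon.

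The cost is an edit to a code list, with no change to design, cohorts or analysis method.
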